4.2.7 Positive results for human immunodeficiency virus (HIV)

4.2.8 Major surgery within 28 days of study day 1

4.2.9 Prophylactic anti-infection vaccination within 1 month prior to starting therapy with AMG 211. Therapeutic vaccination for cancer or infection within 3 months prior to starting therapy with AMG 211.

4.2.10 Currently receiving treatment in another investigational device or drug study, or less than 28 days since ending treatment in another investigational device or drug study. Other investigational procedures while participating in this study are excluded. Exception to this criterion is the participation in the Imaging Study and all procedures related to this study.

4.2.11 Treatment with any chemotherapy, radiotherapy, immunotherapy, biologic, or hormonal therapy for cancer within 14 days prior to study entry **or** not recovered from treatment

4.2.12 Unresolved toxicities from prior anti-tumor therapy, defined as not having resolved to Common Terminology Criteria for Adverse Events (CTCAE), version 4.0 grade 1 or to levels dictated in the eligibility criteria with the exception of alopecia or toxicities from anti-tumor therapy that are considered irreversible (defined as having been present and stable for > 6 months), may be allowed if they are not otherwise described in the exclusion criteria AND there is agreement to allow by both the investigator and the sponsor

4.2.13 Recent history of cardiac disease, including myocardial infarction, unstable angina pectoris, or uncontrolled arrhythmia within 6 months; or evidence of severe congestive heart failure with New York Heart Association ([Appendix G](#)) severity classification > Class I within 12 weeks prior to screening

4.2.14 History or evidence of any other clinically significant disorder, condition or disease (with the exception of those outlined above), that in the opinion of the investigator or sponsor would pose a risk to subject's safety or interfere with the study evaluation, procedures, or completion

4.2.15 Clinical history of significant central nervous system (CNS) pathology (including but not limited to: history of brain metastasis, multiple occurrences of confusion, dementia, previous CNS infarctions, migraine headaches [within 6 months prior to starting therapy with AMG 211], seizure disorder, or major brain surgery)

4.2.16 History of chronic autoimmune disease, eg, rheumatoid arthritis, inflammatory bowel disease, systemic lupus erythematosus, or multiple sclerosis (with the exception of stable type 1 diabetes)

4.2.17 Males or Females of reproductive potential and unwilling to practice an acceptable method of effective birth control while on study through 30 days after receiving the last dose of study drug. Acceptable methods of effective birth control include:

- sexual abstinence (males, females)
- use of a combination of 2 acceptable methods of effective birth control including: bilateral tubal ligation (females), vasectomy (males), oral, transdermal, injected, or implanted contraceptives, intrauterine device, female condom with spermicide, diaphragm with spermicide, contraceptive sponge with spermicide, cervical cap, or use of a condom with spermicide by the sexual partner)

4.2.18 Females who are lactating/breastfeeding or who plan to breastfeed while on study through 30 days after receiving the last dose of study drug

4.2.19 Females with a positive pregnancy test

- 4.2.20 Females planning to become pregnant while on study through 30 days after receiving the last dose of investigational product
- 4.2.21 Subject is likely to not be available to complete all protocol-required study visits or procedures, and/or to comply with all required study procedures to the best of the subject and investigator's knowledge

5. SUBJECT ENROLLMENT

Before subjects begin participation in any study-specific activities/procedures, Amgen requires a copy of the site's written Institutional Review Board/Independent Ethics Committee (IRB/IEC) approval of the protocol, informed consent form (ICF), and all other subject information and/or recruitment material, if applicable (see [Section 11.2](#)). All subjects must personally sign and date the ICF before commencement of study-specific activities/procedures. After meeting all eligibility criteria, a subject is considered enrolled on day 1 (cycle 1 day 1) when the cIV infusion with investigational product is started. The investigator is to document this decision and date in the subject's medical record and in/on the enrollment electronic case report form (eCRF). Adverse events are to be collected for an eligible subject once they are enrolled in the study (from cycle 1 day 1 onwards). Adverse Events occurring during the screening period and which are not related to study procedures will be captured as medical history.

Each subject who enters into the screening period for the study (defined as the point at which the subject signs the informed consent) receives a unique subject identification number before any study procedures are performed. The subject identification number will be assigned manually. This number will be used to identify the subject throughout the clinical study and must be used on all study documentation related to that subject.

PPD

The subject identification number must remain constant throughout the entire clinical study; it must not be changed after initial assignment, including if a subject is rescreened.

All screening tests and procedures should be performed within 21 days before enrollment, unless otherwise noted. All blood and urine samples collected for the

screening assessment (except for biomarkers and soluble CEA [sCEA]) will be submitted and analyzed by the local laboratory. Laboratory assessments used to determine subject eligibility may be repeated once for confirmation (up to a total of 2 times during the screening period), if necessary before the subject is considered a screen failure.

Subjects who do not meet the eligibility criteria within the 21-day screening period will not be eligible for enrollment. Subjects may be re-screened up to 3 times at the discretion of the investigator. The subject must be re-consented if a re-screening attempt occurs outside the screening period. Subjects who are deemed not eligible will be documented as screen failures.

Subjects may be eligible to enroll once all screening tests and procedures are completed and results indicate that all eligibility criteria are met. A site representative will complete and send the enrollment eligibility worksheet to the sponsor or designee along with the lab results and any requested supporting documentation for review of eligibility criteria. The Amgen representative will acknowledge receipt of the paperwork and send confirmation of cohort and dose level assignment for the subject.

5.1 Treatment Assignment

An Amgen representative will notify the site(s) in writing when a cohort is open to screen new subjects. In the dose-escalation cohorts, subjects will be assigned sequentially into cohorts as they open. Three subjects will initially be enrolled into each dose-escalation cohort with at least a 48-hour interval between treatment start of subject 1 and subject 2 of each cohort. In the event that a DLT is observed, 3 additional subjects may be enrolled for a total of up to 6 evaluable subjects. Subjects are considered evaluable, for the purposes of the dose level review of safety information if they receive at least 90% of the planned doses of investigational product or if they have discontinued investigational product due to a DLT. Subsequent cohorts will begin enrollment upon completion of the previous cohort if it is deemed safe to proceed to the next dose level.

Subjects not participating in the Imaging Study will start enrollment into the dose-expansion cohort upon completion of the dose-escalation cohorts. Subjects concurrently participating in the Imaging Study will start enrollment into the dose-expansion cohort while dose-escalation cohorts are still open for enrollment.

The treatment start date is to be documented in the subject's medical record and on the enrollment eCRF.

6. TREATMENT PROCEDURES

6.1 Classification of Product(s) and/or Medical Device(s)

The Amgen Investigational Products used in this study includes AMG 211 and IV bag protectant.

The Investigational Product Instruction Manual (IPIM), a document external to this protocol, contains detailed information regarding the storage, preparation, and administration of AMG 211.

The medical devices used in this study include: portable infusion pump, IV bag, and infusion line including a 0.2 μ m in-line filter.

6.2 Investigational Product

All investigational products will be dispensed at the research facility by a qualified staff member.

A physician or nurse trained in emergency medicine must be available when the infusion of investigational product is started for immediate intervention in case of complications.

6.2.1 Amgen Investigational Product AMG 211 and IV Bag Protectant

AMG 211 and the IV bag protectant will be manufactured by MedImmune Pharma BV, packaged by Amgen Inc. and distributed using Amgen clinical study drug distribution procedures. AMG 211 will be presented as a sterile, single-use, lyophilized formulation for cIV infusion in a 3 mL glass vial containing 0.37 mg AMG 211. The formulation after reconstitution is 0.5 mg/mL in [C] mM sodium citrate/citric acid, [C] mM L-lysine hydrochloride, [C] mM ([C] % w/v) trehalose dihydrate, [C] % (w/v) polysorbate-80 at pH [C].

The IV bag protectant will be presented as a sterile liquid in a 20 **mm** glass vial (**containing 10 mL of IV bag protectant**) intended for pre-treatment of IV bags prior to dilution of AMG 211 drug product. The IV bag protectant does not contain an active pharmaceutical ingredient.

6.2.1.1 Dosage, Administration, and Schedule

AMG 211 will be delivered using preprogrammed infusion pumps approved for use by the appropriate regulatory authority for the country in which the subject is undergoing treatment.

AMG 211 infusion for solution will be prepared in bags for IV infusion. The investigational product will be administered as a cIV infusion at a constant flow rate over 1 to 4 weeks followed by a 3-week (cohort 1 in the dose-escalation cohorts) or 2-week

(all other cohorts) treatment free interval prior to the following treatment cycle. Subjects will be hospitalized on day 1 cycle 1 for a minimum of 72 hours and at all subsequent cycles for a minimum of 48 hours. Subjects can be hospitalized for a longer time period at the discretion of the investigator. If required for logistical reasons (eg, long travel times), subjects may be hospitalized the day before dosing (day -1) of any cycle and at the EOI for cycle 1 for required PK samples. Subjects in the 7- and 14-day schedules will receive AMG 211 for 7 or 14 days followed by 21 days off or 14 days off, respectively (a 28-day cycle). Subjects on a 28-day schedule will receive AMG 211 for 28 days followed by 14 days off (a 42-day cycle).

The planned dose levels for the dose-escalation cohorts are: 200, 400, 800, 1600, 3200, and 6400 µg/d. Alternative dose levels up to 12800 µg/day will be explored in either 14-day or 28-day schedule based on emerging data. The MTD or recommended phase 2 dose will be administered in the dose-expansion cohort.

The infusion start time should be chosen carefully to avoid any interference or inconvenience with time points of safety assessments, PK/PD measurements, and infusion bag changes. The site should record any unscheduled interruption of an infusion on the eCRF, and provide the start and stop date/time of the infusion and the bag change.

AMG 211 should be administered through a central venous access. In the event that administration through a central venous access is not possible, AMG 211 may be administered temporarily through a peripheral venous line if the subject is hospitalized. The final solution for infusion should be administered through a 0.2 µm in-line filter.

Administration of the premedication (eg, dexamethasone) to minimize the risk of cytokine-release syndrome symptoms is recommended for all treatments at a dose of 800 µg/day or higher (see [Section 6.5](#)).

Infusion bags should be changed in accordance with local pharmacy standards for infusion of compounded sterile products up to every 4 days.

After completion of a first cycle without a DLT (may be 2 cycles in cohort 1), additional treatment cycles can be administered as long as in the judgment of the investigator the subject is deriving benefit.

Longer breaks of up to 8 weeks between treatment cycles will be allowed for subjects who remain on study treatment beyond 24 weeks from start of study treatment or in the event of urgent reasons other than adverse events related to study drug. The break

must be agreed upon after consultation with the sponsor and may be done to allow sufficient recovery from adverse events, due to the subject's schedule (eg, going on vacation) or for other reasons requiring a longer break.

The amount of investigational product used in preparation, total volume of preparation, concentration of preparation, quantity, dose, start date/time, stop date/time, and lot number of investigational product are to be recorded on each subject's eCRF.

The effects of overdose of this product are not known.

6.2.1.2 AMG 211 Outpatient Dosing

If deemed stable by the investigator, a subject may continue AMG 211 cIV infusion as an outpatient. In the outpatient setting, the subject will either return to the study site for infusion bag changes or the subject will be visited by a well-trained ambulant/home care service provider at specific intervals to change the infusion bag, **measure vital signs**, monitor and document adverse events and/or serious adverse events, and document any issues with the cIV infusion or infusion pump. The subject and ambulant/home care service provider will be trained and will receive written instructions for storage of the IV bags. The ambulant/home care service provider will complete source documentation before any study-related tasks are started.

In addition to visits, the ambulant/home care service provider **or study site personnel** will also contact the subject by telephone to monitor and document adverse events and/or serious adverse events and to document any issues with the cIV infusion or infusion pump. During cycle 1, the ambulant/home care service provider **or study site personnel** will contact the subject on each day that the subject is not hospitalized. Starting with cycle 2, the ambulant/home care service provider **or study site personnel** will contact the subject every 2 days except on those days that the subject will be visited to change the infusion bag.

Refer to the home health care manual for detailed information on the storage, handling, and administration of AMG 211, mandatory procedures, and data collection requirements.

Following each visit or telephone contact, the information collected will be documented on the Ambulant/Home Care Services visit worksheet and forwarded to the investigator. Any unexpected or unusual events as well as any deviations will be communicated promptly to the investigator. If any adverse event occurs in the outpatient setting, the ambulant/home care service provider should directly contact the site for further

management. The ambulant/home care service professionals provide 24 hour emergency on-call service. In the event of an interruption of the AMG 211 clV infusion of > 24 hours, the restart of the infusion should be performed in the clinic/hospital under the supervision of the investigator or designee. Prophylactic treatment with steroid (eg, dexamethasone) is recommended before restarting of AMG 211 if clinically indicated.

6.2.1.3 Dose-cohort Study Escalation and Stopping Rules Dose-limiting Toxicities (DLT)

A DLT will be defined as any of the following occurring in a subject during the first 28 days of treatment and regarded by the investigators and/or sponsor to be related to AMG 211. The Common Terminology Criteria for Adverse Events (**CTCAE** version 4.03) will be used to assess toxicities/adverse events.

Hematological DLTs

- ANC < $0.5 \times 10^9/L$ for ≥ 7 days
- Febrile neutropenia (fever of unknown origin without clinically or microbiologically documented infection) with ANC < $0.5 \times 10^9/L$ and fever $\geq 38.5^{\circ}\text{C}$
- Platelets < $25 \times 10^9/L$ ≥ 7 days

Non-hematological DLTs

Any AMG 211-related \geq grade 3 non-hematological toxicity excluding

- Nausea and vomiting, which is not refractory to anti-emetics
- Flare-up of pain because of potential increase in tumor volume is not regarded as a DLT
- Cytokine release syndrome manageable with symptomatic treatment and/or infusion interruption of up to 2 days

Subjects are evaluable for a DLT when they have received at least 90% of the planned doses of investigational product within the first treatment cycle (first 28 days of a cycle independent of length of the infusion) with or without the occurrence of a DLT in the 28-day safety observation period.

Any adverse event occurring outside the DLT window that is determined by the investigator to be possibly related to the investigational product, which is seen more frequently or more severe than expected or is persistent despite appropriate management, can be determined to be a DLT upon unanimous decision by the DLRT after review of the adverse event and all available safety data.

For certain toxicities such as laboratory abnormalities without a clear clinical correlation (eg, increase in serum lipase level without signs or symptoms of a clinical pancreatitis), a

discussion between the investigator and the sponsor may take place whether that adverse event should be assessed as a DLT.

6.2.1.4 Dosage Adjustments, Delays, Rules for Withholding or Restarting, Permanent Discontinuation

6.2.1.4.1 Dose Reduction

Hematological criteria for dose reduction are presented in [Table 4](#) and non-hematological criteria are presented in [Table 5](#). Dose reduction is possible with re-treatment at 1 dose level lower ([Table 5](#))

Table 4. Hematological Criteria for Dose Reduction

CTCAE Grade	ANC ($10^9/L$)	Platelets	Dose Delay ^a	Dose Reduction
Hematological				
0-2	> 1.0	> 50	Continue infusion	No change
3	< 1.0 – 0.5	< 50 – 25	Continue infusion until Investigator assesses toxicity to require interruption	No change
4	< 0.5	< 25	Delay until \leq grade 2	Restart at 1 dose level lower

Table 5. Non-hematological Criteria for Dose Reduction

CTCAE Grade	Dose Delay	Dose Reduction	Comment
Non-hematological			
Infection, cytokine release syndrome, tumor lysis syndrome, diarrhea, hypoxia			
2	Delay until ≤ grade 1	No change	Restart in hospital
3	Delay until ≤ grade 1	Restart at 1 dose level lower	Consider re-escalation if completely recovered and no new toxicity occurred within 7 days of infusion. Permanent discontinuation of study treatment if no recovery within 21 days. Start at the same dose if resolved cytokine release syndrome, infection, tumor lysis syndrome, or hypoxia.
4	Discontinue infusion	Permanent discontinuation of study treatment	-
All other non-hematological toxicities and clinically significant laboratory parameters			
0-2	Continue infusion	No change	Interruption can be considered if deemed necessary by the investigator
3	Delay until ≤ grade 2	Resolution to grade 1 or 2: Restart at 1 dose level lower Resolution to normal within 1 week or a relationship to study drug can be ruled out: No change	Per the Investigator medical discretion to decide whether to continue the infusion for up to 72 hours if toxicity has not occurred during the DLT window and if the toxicity or abnormal labs are responding to treatment or represents an asymptomatic laboratory change. Permanent discontinuation of study treatment if no recovery within 21 days
4	Discontinue infusion	Permanent discontinuation of study treatment	-

ANC = absolute neutrophil count; CTCAE = Common Terminology Criteria for Adverse Events;

DLT = dose-limiting toxicity

^a Applies to all hematologic toxicity that persists for > 24 hours despite appropriate treatment

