6.2.1.4.3 Restarting the Infusion

Treatment may resume if the interruption is \leq 21 days and if:

- The interruption occurred due to other reasons than toxicity (technical or logistic reasons; eg, diagnostic measurements). The infusion can be restarted at the same dose and without additional measures.
- The toxicity has resolved to \leq grade 1. The infusion can be restarted according to guidelines presented in [Table 4](#) or [Table 5](#).
- The toxicity occurred during the DLT period or has resolved to grade 2. The infusion can only be restarted in an individual subject with a clear clinical benefit from treatment after consultation with the sponsor on a case-by-case basis.

Restarting the infusion after a treatment interruption requires care. The start should be performed in the hospital with all infusion day 1 specific measures if the reason for the interruption was other than a technical issue or the interruption was $>$ 24 hours independent of reason. Prophylactic treatment with steroid (eg, dexamethasone) is recommended before restarting of AMG 211 if clinically indicated.

Subjects that have had a treatment interruption during cycle 1 should be given the opportunity to complete a total of 14 or 28 days of infusion even though these may not be DLT evaluable subjects.

Subjects that have had a treatment interruption lasting \geq 48 hours from cycle 2 onwards should re-start treatment as a new cycle.

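### Table 4 directs a lower-dose restart after a grade 4 cytopenia in cases where Sections 6.2.1.4.3 and 6.2.1.4.4 require a stop or allow restart only with clear benefit and sponsor consultation

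*Protocol*

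**What the plan says.** Four parts of protocol Section 6.2.1 bear on a subject with a grade 4 cytopenia (ANC below 0.5 or platelets below 25, × 10^9/L).

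- **Table 4 (6.2.1.4.1), grade 4 row.** Delay until grade 2 or lower, then "Restart at 1 dose level lower". The sentence introducing the tables says only "Dose reduction is possible with re-treatment at 1 dose level lower" and sets no order of precedence. Footnote a to the dose-delay column reads "Applies to all hematologic toxicity that persists for > 24 hours despite appropriate treatment".
- **6.2.1.4.3, Restarting the Infusion.** The interruption may last at most 21 days. The second bullet covers toxicity resolved to grade 1 or lower: "The infusion can be restarted according to guidelines presented in" Table 4 or Table 5. The third bullet covers a different set, "The toxicity occurred during the DLT period or has resolved to grade 2", and says that the infusion "can only be restarted in an individual subject with a clear clinical benefit from treatment after consultation with the sponsor".
- **6.2.1.4.4, Permanent Discontinuation.** A DLT ends treatment. A lower-dose restart can be considered only if there is clear clinical benefit, the toxicity has resolved and the sponsor has been consulted.
- **6.2.1.3, DLT definition.** The hematological DLTs are ANC below 0.5 for at least 7 days, platelets below 25 for at least 7 days, and "Febrile neutropenia (fever of unknown origin without clinically or microbiologically documented infection) with ANC" below 0.5 and fever. The window is the first 28 days, but the Dose Level Review Team (DLRT) can unanimously declare a later event a DLT.

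**The concern.** Every hematological DLT uses a grade 4 cut-off, so every one falls in Table 4's grade 4 row. For a subject without clear benefit, that row says restart while 6.2.1.4.4 says stop. A second mismatch is the recovery threshold. Table 4 accepts grade 2, whereas 6.2.1.4.3 refers sites to the table only at grade 1 or lower and makes a grade 2 restart conditional.

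A site that works from the table could re-expose a subject to the drug after a hematological DLT with no evidence of benefit and no call to the sponsor. The layout makes this plausible. Table 5 writes limits of this kind into its cells (the DLT window, no recovery within 21 days), and Table 4 does not, so a reader could take Table 4's row as complete.

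**Working it through.** The plan gives no figure to reproduce and no rate of grade 4 cytopenia, so the check sets the rules side by side.

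**Step 1: does a hematological DLT reach the grade 4 row?** The cut-offs are the same (6.2.1.3 and Table 4). The two duration-based DLTs last at least 7 × 24 = 168 hours, which always exceeds the 24 hours in footnote a. Febrile neutropenia carries no minimum duration, so it exceeds 24 hours only if it persists.

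**Step 2: compare the rules.** Take a subject with no clear benefit and an interruption of at most 21 days. There are 4 event types and 2 recovery grades, so 4 × 2 = 8 combinations. Table 4 read alone restarts all 8.

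| Event | Recovery | 6.2.1.4.3 | 6.2.1.4.4 | Result |
|---|---|---|---|---|
| DLT, first 28 days | grade 2 | bullet 3 bars | stop | conflict |
| DLT, first 28 days | grade 1 or lower | bullet 2 points to Table 4; bullet 3 bars | stop | conflict |
| Later DLT declared by DLRT | grade 2 | bullet 3 bars | stop | conflict |
| Later DLT declared by DLRT | grade 1 or lower | bullet 2 points to Table 4; bullet 3 does not apply | stop | conflict |
| Not a DLT, first 28 days | grade 2 | bullet 3 bars | no DLT trigger | conflict with bullet 3 |
| Not a DLT, first 28 days | grade 1 or lower | bullets 2 and 3 both met | no DLT trigger | ambiguous |
| Not a DLT, later | grade 2 | bullet 3 bars | no DLT trigger | conflict with bullet 3 |
| Not a DLT, later | grade 1 or lower | bullet 2 points to Table 4 | no DLT trigger | consistent |

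Tally: 4 conflict with 6.2.1.4.4, 2 conflict with bullet 3 only, 1 is ambiguous and 1 is consistent; 4 + 2 + 1 + 1 = 8. These are combinations of rules, not frequencies.

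**Step 3: does any text settle the order?** None does for hematological toxicity. Section 6.4.3 says that subjects who meet 6.2.1.4.4 must not be rechallenged, but it sits under the hepatotoxicity rules.

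**Step 4: how often might it arise?** Section 2.2.4 lists 4 first-in-human DLTs: hypoxia 2, diarrhea 1, cytokine release syndrome 1. None was hematological. About 32 subjects in this study had no DLT by April 2016, at doses up to 6400 µg. Escalation to 12800 µg/day is still planned, so the rule may yet be needed.

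**The case against.** The strongest reply is that the section works when read as a whole. Table 4 is headed as dose-reduction criteria and its introduction is permissive. Whether a subject may restart is a matter for 6.2.1.4.3 and 6.2.1.4.4, and for a hematological DLT in the first 28 days without clear benefit, bullet 3 and 6.2.1.4.4 agree that there is no restart. Harm then requires a site to read one cell and ignore the two subsections on restart and discontinuation. A restart for toxicity also has in-hospital protection ("The start should be performed in the hospital with all infusion day 1 specific measures"), the sponsor may take part in judging relatedness (6.2.1.3), and the DLRT reviews DLTs and other toxicity of grade 3 or higher (10.3.2).

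Much of this stands, and it rules out two stronger readings.

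- **A reader might infer that Table 4 restarts treatment without any condition.** It does not. The row requires recovery to grade 2 or lower, and 6.2.1.4.3 adds the 21-day limit. What the row lacks is a DLT, clear-benefit or sponsor-consultation condition.
- **A reader might infer that every grade 4 cytopenia in the DLT period should need clear benefit before restart.** The documents do not settle this for a non-DLT event that recovers to grade 1 or lower. Section 6.2.1.4.3 also wants subjects interrupted in cycle 1 to be able to complete their 14 or 28 days of infusion. First imaging is normally at 8 to 10 weeks, or 10 to 12 weeks on the 28-day schedule (7.3.6), so benefit can rarely be shown within 28 days.

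The reply does not remove the inconsistency. For a DLT resolved to grade 1 or lower, bullet 2 itself sends the site back to Table 4 while 6.2.1.4.4 requires a stop. For a later DLT declared by the DLRT, bullet 3 does not intervene. Hospital restart and DLRT review are real safeguards, but neither makes benefit or consultation a condition of that subject's restart.

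**Conclusion.** The point holds as an internal inconsistency in a safety rule. In the grade 4 row, Table 4 followed as written restarts a subject with a DLT whom 6.2.1.4.4 requires to stop, and restarts at grade 2 a subject whom 6.2.1.4.3 allows to restart only with clear benefit and sponsor consultation.

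Its practical size is small: hematological DLTs look uncommon so far, and the surrounding text gives the right answer to a careful reader in most cases. No endpoint, sample size or error rate changes. The conclusion rests on three readings: that the DLT period in bullet 3 means the 28-day window, that Table 4's row can be followed by itself because no precedence is stated, and that the subject has no clear clinical benefit. It is worth correcting because the consequence falls on an individual subject and the correction is wording.

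**What to change.** 1. In 6.2.1.4.1, state that Tables 4 and 5 set the dose on restart and apply subject to 6.2.1.4.3 and 6.2.1.4.4, which prevail on whether a restart is allowed. Word this so that it does not loosen Table 5's permanent stop for grade 4 non-hematological toxicity.
2. Add to Table 4's grade 4 row: *If the event is a DLT, or has resolved only to grade 2: restart only with clear clinical benefit and after sponsor consultation (for a DLT, only once resolved); otherwise discontinue.*
3. Separately, the sponsor should state whether bullet 2 or bullet 3 of 6.2.1.4.3 governs a non-DLT grade 4 cytopenia in the DLT period that resolves to grade 1 or lower. The stricter reading should not be the default: it could end treatment after a brief cytopenia in cycle 1.

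Cost: one sentence, one table cell and one clarification in the protocol. A few subjects lose an automatic restart.

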6.2.1.4.2 Infusion Interruption

Significant events requiring a change in treatment will be managed by immediate infusion interruption of equal or less than 24 hours. Both, infusion interruptions and treatment interruptions greater than 24 hours, have to be documented in the eCRF:

- The subject experiences a DLT as defined in [Section 6.2.1.3](#)
- The subject meets criteria for temporary or permanent discontinuation of investigational product as described in [Section 8.3](#)
- Technical problem with the infusion pump
- The investigational product is incorrectly prepared or administered (eg, overdose)

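### For a grade 3 non-hematological DLT, Table 5 allows a same-dose restart in two places, while 6.2.1.4.4 allows only a stop or a lower-dose restart

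*Protocol*

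**What the plan says.** **DLT definition (Protocol 6.2.1.3).** The window is the first 28 days. A non-hematological DLT is a related event of at least "grade 3 non-hematological toxicity excluding" three items. The only one of these that bears on the toxicities named in Table 5 is "Cytokine release syndrome manageable with symptomatic treatment and/or infusion interruption of up to 2 days". Grade 3 hypoxia, infection and tumor lysis syndrome are not excluded as such.

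**Table 5 (6.2.1.4.1), grade 3, row for infection, cytokine release syndrome (CRS), tumor lysis syndrome, diarrhea and hypoxia.** The Dose Reduction column says "Restart at 1 dose level lower". The Comment column ends with "Start at the same dose if resolved cytokine release syndrome, infection, tumor lysis syndrome, or hypoxia". Diarrhea is not in that sentence.

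**Table 5, grade 3, row for all other non-hematological toxicities.** The restart is one level lower if the event resolves to grade 1 or 2. The dose is unchanged if it resolves to normal within 1 week, or if a relation to study drug is ruled out.

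**Restarting (6.2.1.4.3).** Bullet 2 covers toxicity resolved to grade 1 or less: "The infusion can be restarted according to guidelines presented in" Table 4 or Table 5. Bullet 3 covers toxicity in the DLT period, or toxicity resolved only to grade 2: "The infusion can only be restarted in an individual subject with a clear clinical benefit from treatment after consultation with the sponsor". Bullet 3 gives no dose.

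**Permanent discontinuation (6.2.1.4.4).** A DLT leads to permanent discontinuation. The one exception is a lower-dose restart for a subject with clear clinical benefit whose toxicity has resolved, after consultation with the sponsor.

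The SAP takes the DLT definition from the protocol and does not address restart doses.

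**The concern.** One event can fall under all of these rules. A related grade 3 hypoxia in cycle 1 that resolves completely is a DLT, unless it is judged part of manageable CRS. It also sits in the first grade 3 row of Table 5, and it meets the conditions of both bullet 2 and bullet 3 of 6.2.1.4.3. The Table 5 comment then gives the same dose, and 6.2.1.4.4 gives a stop or a lower dose. Both cannot be followed. A related grade 3 event of another type that normalises within a week meets the same conflict in the other row.

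At stake is the dose at which a subject is re-exposed after a dose-limiting event. The dose-toxicity model is not affected, because the event is counted as a DLT whatever happens next.

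**Working it through.** There is no statistical figure to reproduce for the rule itself, so the check sets the texts side by side and then sizes the difference.

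**1. Where a DLT meets a same-dose instruction**

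| Event, if it is a DLT | Table 5 restart dose | 6.2.1.4.4 | Clash on dose? |
|---|---|---|---|
| Grade 3 hypoxia, infection, tumor lysis syndrome, or CRS that is not manageable; resolved | Column: one level lower. Comment: same dose | Stop, or lower dose | Yes, through the comment |
| Grade 3 diarrhea, resolved to grade 1 or less | One level lower | Stop, or lower dose | No |
| Other related grade 3, normal within 1 week | Unchanged | Stop, or lower dose | Yes |
| Other related grade 3, resolved to grade 1 or 2 | One level lower | Stop, or lower dose | No |
| Any grade 4 non-hematological | None; permanent stop | Stop, or lower dose | No same-dose option |

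Manageable CRS, unrelated events, and events after day 28 that the dose level review team does not declare DLTs are not DLTs, so they lie outside the point.

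**2. Whether another section settles it**

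- 6.2.1.4.3 bullet 2 refers to Table 5 and has no DLT exception.
- 6.2.1.4.3 bullet 3 limits who may restart, but not at what dose.
- 6.2.1.1 ties further cycles to a first cycle without a DLT. This supports the stricter rule, but Table 5 does not refer to it.
- No section says which rule prevails.

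**3. Size of the difference in dose**

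Inputs (Protocol 2.2.3): clearance 2.3 L/hr, or 55.2 L/day. Formulas: steady-state concentration = daily dose / 55.2; daily AUC = daily dose / 2.3.

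| Dose (µg/day) | Steady state (ng/mL) | Daily AUC (hr·ng/mL) |
|---|---|---|
| 3200 | 3200 / 55.2 = 58.0 | 3200 / 2.3 = 1391 |
| 6400 | 6400 / 55.2 = 115.9 | 6400 / 2.3 = 2783 |
| 12800 | 12800 / 55.2 = 231.9 | 12800 / 2.3 = 5565 |

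These agree with Protocol Table 2 (58, 116 and 232 ng/mL; 1391, 2783 and 5565 hr·ng/mL). Adjacent levels differ by a factor of 2 (6400 / 3200 = 12800 / 6400 = 2). Section 6.2.1.4.4 gives no size for the lower dose, so one planned level down is an assumption.

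**4. How often the conflict could arise**

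Restart requires an interruption of at most 21 days (6.2.1.4.3). A DLT on the last day of the window would therefore restart by about day 28 + 21 = 49. The first scheduled on-treatment scan is at 8 to 10 weeks (from day 8 × 7 = 56), or at 10 to 12 weeks on the 28-day schedule (from day 10 × 7 = 70), per 7.3.6. Clear benefit would thus usually have to be shown before any scheduled scan. The exception is a later event that the dose level review team declares a DLT. About 32 subjects at up to 6400 µg/day had no DLT by April 2016 (2.2.4).

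**The case against.** The strongest reply is that the specific rule overrides the general one. Table 5 is a grid by grade for all cycles. Section 6.2.1.4.3 bullet 3 deals separately with toxicity in the DLT period, and 6.2.1.4.4 gives the only restart dose written for a DLT. Read that way there is one answer, the sponsor is consulted every time, and what is missing is a cross-reference. Most of this stands: it is the sensible reading, and it keeps the practical reach small. It does not remove the conflict. The protocol does not state the precedence, and bullet 2 sends the reader to Table 5 for the dose.

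Four stronger readings are tempting, and the documents do not support them:

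- *Table 5 as a whole prescribes the same dose.* In the first row the Dose Reduction column says one level lower; only the comment departs from it.
- *The other row has a DLT safeguard that this row lacks.* The condition "if toxicity has not occurred during the DLT window" governs only whether the infusion may continue for up to 72 hours. That row's unchanged-dose restart has no DLT exception either.
- *A DLT is listed under 6.2.1.4.2 ("The subject experiences a DLT as defined in" 6.2.1.3), so a restart is foreseen.* The same list includes criteria for permanent discontinuation, so being listed implies no restart.
- *A site could restart at full dose on its own.* Bullet 3 requires clear benefit and sponsor consultation.

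The two grade 3 hypoxia DLTs in the first-in-human study (2.2.4) show that the event type is plausible for this molecule. They followed 3-hour infusions before steroid prophylaxis was added, so they give no rate for continuous infusion.

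**Conclusion.** The inconsistency is real and sits in current text. For a grade 3 non-hematological DLT, Table 5 permits a same-dose restart in two places, bullet 2 of 6.2.1.4.3 leads there, and 6.2.1.4.4 does not allow it. The evidence favours the stricter rule as the intended one. What stays open is the dose after sponsor consultation, not whether a site may restart unaided.

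The difference is 2-fold in predicted exposure if the lower dose means one planned level. Where there is no clear benefit, the stricter rule is to stop. The 2-fold figure is the spacing of the dose ladder and does not measure risk; the documents give no rate for these events under continuous infusion. The 12800 µg/day level lies above the April 2016 experience. Overall this is a low-frequency safety inconsistency, minor to moderate, with no effect on any endpoint or on the dose-toxicity model.

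**What to change.** - Add a footnote to the whole of Table 5, not only to one row, and the same clause to 6.2.1.4.3 bullet 2. Suggested text: *Same-dose or no-change restart does not apply when the event is a DLT; 6.2.1.4.3 bullet 3 and 6.2.1.4.4 then govern (stop, or restart at a lower dose only).*
- In 6.2.1.4.3 bullet 3, state that a restart after a DLT is at a lower dose. Limit this to DLTs, because the bullet also covers other toxicities.

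The cost is a few lines of text, by amendment or clarification letter. No procedure, visit, data item or analysis changes.
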